9 STUDY PROCEDURES

9.1 STUDY SCHEDULE

Table 1: Study Visit Schedule

Note: The fellow eye should be followed per the PI's usual practice based on the ocular health of the fellow eye.

PROCEDURE	SCREENING (DAY -45 TO -6)	BASELINE (DAY -7 TO 0)	SURGERY (DAY 0)	1 DAY (DAY 1)	1 Wk (DAY 5-9)	1 M (DAY 21-35)	3 M (DAY 70-98)	6 M (DAY 150-210)	12 M (DAY 330-420)	12 M WASHOUT ²⁹ (DAY 330-420)
Informed Consent	X									
Demographics	X									
Medical & Ocular History	X	X								
Medication Log	X	X	X	X	X	X	X	X	X	X
BCVA (ETDRS), with manifest refraction	X	X			X	X	X	X	X	
Visual Field (Humphrey 24-2 SITA)	X									X
IOP (Goldmann)	X			X	X	X	X	X	X ³⁰	
Unmedicated diurnal IOP (Goldmann)		X							X ³¹	X
Slit Lamp Exam	X	X		X	X	X	X	X	X	
Gonioscopy	X				X	X	X	X	X	
Dilated Fundus Exam/C:D Ratio	X								X	
Eligibility Assessment	X	X								
Cataract Extraction + ab-interno transluminal viscoelastic delivery and trabeculotomy			X							
AE Assessment	X	X	X	X	X	X	X	X	X	X

²⁹ The 12 month washout visit is only required for subjects who are taking hypotensive medications at the 12 month visit.

³⁰ This is only required for subjects who are taking hypotensive medications at the 12 month visit.

³¹ If subject is not on any hypotensive medications, a diurnal IOP measurement should be obtained at the 12 month visit as unmedicated IOP.

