A record of all ocular hypotensive medications added, discontinued or changed will be documented on the appropriate Case Report Form for each scheduled visit or on a Case Report Form for an Unscheduled Visit, if necessary.

Another potential reason for intervention is hypotony. Intervention should only be considered if the hypotony has caused or is likely to cause sequelae such as a flat chamber. No intervention is indicated when the vision is unchanged from screening, there is no persistent choroidal detachment, the anterior chamber is not flat with lens corneal touch, or the patient is asymptomatic. No intervention should be undertaken for hypotony which is not causing, or threatening to cause, a reduction in vision.

Secondary IOP-Lowering Interventions to Control IOP

If the subject requires another glaucoma procedure to control their IOP, the subject should continue to be followed according to standard of care until the adverse event resolves or 1 month post-re-intervention, whichever is longer. Following this, the subject should be withdrawn from the study.

Subjects who have a secondary IOP-lowering intervention will be considered treatment failures for the purpose of the secondary endpoint analyses. These subjects will be included in the Safety Endpoint analyses through their withdrawal from the study.

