11.2 ANALYSIS POPULATIONS

The intent-to-treat (ITT) analysis population includes all subjects who are enrolled and treated, regardless of whether or not they have a protocol deviation. Due to the eligibility revision in May of 2019 on requiring at least one ocular hypotensive medication, the modified ITT (mITT) population includes all ITT except for the treated eyes that were not on any ocular hypotensive medication at the screening visit. The per-protocol analysis population (PP) is a subset of mITT, which includes all subjects who have taken at least one ocular hypotensive medication at screening and have uneventful cataract extraction followed by ab-interno transluminal viscoelastic delivery and trabeculotomy, 12 month IOP and medication data, and have no clinically significant protocol deviations. It should be noted that the mITT subjects with an uneventful study procedure but with SSIs before the 12-month visit will be included in the PP population even if they do not have the 12-month IOP and medication data. The primary analyses on the primary and secondary endpoint analyses will be carried out on the per-protocol population.

The safety data will be summarized based on the ITT population. The primary and secondary endpoint analyses will also be performed on the mITT population.

The data will be listed separately for the enrolled subjects that are not treated with OMNI and treated subjects that do not have ocular hypotensive medications at the screening.

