11.4 EFFECTIVENESS ENDPOINTS AND ANALYSIS METHODS

Descriptive statistics on continuous variables will include mean, standard deviation, median, minimum, and maximum. Confidence intervals for change from baseline will be included for selected endpoints. Categorical variables will be summarized using frequency counts and percentages. Exact confidence intervals for point estimates may be provided. Statistical testing will be one-sided with a significance level of 0.025 or two-sided significance level of 0.05) unless specify otherwise. Data listings of individual subject data may be provided.

As described above, the primary analyses of the primary and secondary effectiveness endpoints will be based on the PP population (Section 11.2), although the analyses will also be performed on the mITT population. The safety data will be summarized based on the ITT population.

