11.4.1 PRIMARY EFFECTIVENESS ENDPOINTS

The IOP reduction from baseline to 12 months postoperatively and the reduction in number of IOP-lowering medications from baseline to 12 months will be calculated for each eye and summarized descriptively. The 95% confidence interval of the mean reduction will be derived based on the t-distribution. The one-sample t-test will be performed for testing the statistical hypotheses described in Section 11.1.1. It should be noted that, for eyes with secondary surgical interventions (SSI) to control IOP or with SSI that can affect the IOP before 12 months, the last available observed data before the SSI will be used to impute the 12-month data. For the analyses based on the mITT population, the following imputation for subjects with missing 12-month data but without SSI may be performed:

- The within-eye worst IOP (collected after 3 months postoperatively or IOP at baseline for the subjects with no data after postoperative 3 months) for the missing 12-month IOP and worst number of IOP lowering medications (collected after 3 months postoperatively or IOP-lowering medication data at baseline for the subjects with no data after postoperative 3 months) for the missing 12-month number of IOP-lowering medications.
- The worst IOP (collected after 3 months postoperatively or IOP at baseline for the subjects with no data after postoperative 3 months) during the study for the missing 12-month IOP and worst number of IOP-lowering medications (collected after 3 months postoperatively or IOP-lowering medication data at baseline for the subjects with no data after postoperative 3 months) during the study for the missing 12-month number of IOP-lowering medications.
- The mean IOP during the study for the missing 12-month IOP and mean number of IOP-lowering medications during the study for the missing 12-month number of IOP-lowering medications.
- The last-observed-carry-forward approach.

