11.4.2 SECONDARY EFFECTIVENESS ENDPOINT

The number and percent of eyes achieving the secondary effectiveness endpoint will be calculated. The binomial distribution will be used to derive the exact 95% confidence interval of the percent and to perform the statistical hypotheses for the secondary effectiveness endpoint described in Section 11.1.2. It should be noted that, for eyes with secondary surgical interventions (SSI) to control IOP or with SSI that can affect the

IOP before 12 months, the non-responder (i.e. do not achieve the secondary effectiveness endpoint) will be assumed for the missing 12-month response.

For the analyses based on the mITT population, the IOP and number of IOP-lowering medications imputation for missing data described in Section 11.4.1 will be used to derive the corresponding response of the secondary effectiveness endpoint.

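### For eyes with a pressure-affecting second surgery, Section 11.4.1 fills in the 12-month unmedicated IOP from the last earlier data without requiring an off-medication reading

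*Combined protocol and SAP*

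**What the plan says.** The first co-primary endpoint (Sections 7.1 and 11.1.1) is the fall in unmedicated diurnal IOP from baseline to month 12. It is tested against 6.5 mmHg with a one-sample t-test at one-sided 0.025.

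For eyes with an SSI to control IOP, or one that can affect IOP, Section 11.4.1 states that "the last available observed data before the SSI will be used to impute the 12-month data". It attaches no condition on drug use, washout or diurnal averaging, and no other section supplies one.

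These eyes count in the primary test. Section 11.2 says that they "will be included in the PP population even if they do not have the 12-month IOP and medication data", and Section 11.4 says that "the primary analyses of the primary and secondary effectiveness endpoints will be based on the PP population". Many will have no month-12 value: Section 9.9 follows a re-operated subject until the event resolves or for one month, whichever is longer, and then says "Following this, the subject should be withdrawn from the study".

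In Table 1 (Section 9.1), the row that begins "Unmedicated diurnal IOP (Goldmann" is marked only at baseline and at the two 12-month visits. From Day 1 to month 6 the only IOP scheduled is the ordinary Goldmann measurement, with no washout. Section 9.9 advises against IOP-lowering drugs after surgery unless medically warranted, but leaves restarting them to the investigator, in the classes used before surgery.

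On the secondary endpoints the rule is different. Section 9.9: "Subjects who have a secondary IOP-lowering intervention will be considered treatment failures for the purpose of the secondary endpoint analyses". Section 11.4.2 likewise says that non-responder status "will be assumed for the missing 12-month response".

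**The concern.** The baseline value is a washed-out mean of three readings taken over a day (Section 20.5). The carried value may be one visit's reading taken on drops. Subtracting the second from the first counts the effect of the drops as an effect of surgery.

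A hypothetical eye shows how. Baseline is 30 mmHg and the last reading before the SSI is 23 mmHg on drops. The eye enters with a 7 mmHg reduction, above the 6.5 mmHg benchmark. If the drops account for 3 mmHg, the off-drug reduction is 30 - (23 + 3) = 4 mmHg.

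The plan observes this distinction elsewhere. Section 11.6 separates 6-month measurements from the washed-out 12-month IOP, and Section 11.4.4 restricts its by-visit responder outcomes to eyes on no IOP-lowering drugs. At stake is a possible bias in the device's favour, in eyes that went on to further surgery, within a test designed to detect a difference of only 1.0 mmHg (7.5 against 6.5).

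**Working it through.** **1. The plan's own figure.** Inputs from Section 11.1.1: null mean 6.5, alternative 7.5, SD 3.8, one-sided 0.025. Exact power from the noncentral t distribution with n = 116 is 80.25%, so the stated 116 eyes and 80% reproduce. The standard error is 3.8/√116 = 0.353 mmHg.

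**2. Shift in the mean.** Let k be the number of SSI eyes whose carried reading was medicated, and d the amount in mmHg by which that reading lies below the true off-drug value. The mean reduction is overstated by k × d/116.

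Neither k nor d is in the documents. The nearest figure is inclusion criterion 5 (Section 8.1), which requires baseline unmedicated IOP to be at least 3 mmHg above screening IOP. That is a preoperative figure and not a floor after surgery. The 8 mmHg value is an assumption with no source.

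**3. Error of this one test when the true overall mean is 6.5.** Simulation: 200,000 runs per cell, n = 116, normal with SD 3.8, SD re-estimated in each run. With no affected eyes it returns 0.025.

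| k | shift, d = 3 | error, d = 3 | shift, d = 8 | error, d = 8 |
|---|---|---|---|---|
| 1 | 3/116 = 0.026 | 0.029 | 8/116 = 0.069 | 0.036-0.039 |
| 3 | 9/116 = 0.078 | 0.039 | 24/116 = 0.207 | 0.069-0.083 |
| 6 | 18/116 = 0.155 | 0.060 | 48/116 = 0.414 | 0.159-0.211 |

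The d = 3 column takes the SSI eyes' true off-drug reduction to average 6.5 mmHg, as in the other eyes. In the d = 8 column, the lower figure makes the same assumption. The upper figure takes it to average 0, with the overall mean held at 6.5. An average of 3 falls between (0.038, 0.079, 0.195). As a check on d = 3, shifting the mean and holding the SD at 3.8 gives 0.030, 0.041 and 0.064.

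**4. Whether another planned analysis would reveal the problem.** The SSI sentence in Section 11.4.1 is not confined to the per-protocol set, so the mITT analysis inherits it. The four optional mITT imputations cover only eyes without an SSI. Section 11.4.4 tabulates 12-month IOP by SSI and plots time to SSI, but does not repeat the primary test.

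**5. Cost of a conservative alternative.** Suppose each affected eye takes the higher of its medicated reading and its baseline, so that it is credited with no reduction. At a true overall mean of 7.5, with these eyes' true off-drug reduction averaging 3 mmHg, power for k = 1, 3, 6 is 78%, 71% and 60%. With their true off-drug values it would be 80%, 79% and 78%.

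The alternative can over-correct. If six eyes are credited with 8 mmHg each, of which 3 is drug, the mean loses 6 × 8/116 = 0.41 mmHg to remove a bias of 6 × 3/116 = 0.16.

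**The case against.** The strongest reply is that Section 11.4.1 does not say which variable is carried. The endpoint is unmedicated diurnal IOP, and the last such value before an SSI is normally baseline. Read that way, the eye is credited with no reduction and the rule is already conservative. This cannot be excluded. However, the mITT imputations in the same section name baseline only as a fallback when nothing was collected after month 3, which suggests that ordinary visit readings are meant. Either way the text needs to say.

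Secondly, an SSI to control IOP tends to follow a high reading, and a reading that helped to prompt surgery may be unusually high. That works against the device. The rule also covers SSIs done for other reasons, where the eye may be off drops. A reader might infer that the primary test is biased in the device's favour overall. The documents support less: a medicated reading overstates the reduction relative to that eye's off-drug value, but the net direction across SSI eyes is uncertain.

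Thirdly, a reader might infer that the plan contradicts itself by failing these eyes on the secondary endpoints but not on the primary. The secondary endpoints are binary; a continuous endpoint needs a number, and using data from before the SSI at least keeps the second operation's benefit from being credited to the device. The missing piece is the medication condition.

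Finally, the carried drug count works against the device on the second co-primary, and Section 11.1.1 requires both to succeed. That limits the consequence for the trial but does not correct the IOP test.

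**Conclusion.** The concern holds as a gap in the specification of the primary analysis that should be fixed. Section 11.4.1 allows a medicated reading to stand in for unmedicated diurnal IOP in SSI eyes, and no planned re-test would show the effect.

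Its size is unknown. Under an assumed 3 mmHg in 1, 3 or 6 of 116 eyes, the mean shifts by 0.03, 0.08 or 0.16 mmHg and the one-sided error of this test is about 3%, 4% or 6%. An assumed 8 mmHg gives about 4%, 7-8% or 16-21%. These figures isolate the drug effect and do not offset it by any selection of high readings. If SSIs are rare, the effect is small.

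A reader might take the upper figures as the trial's false-positive rate. They are not: they need six medicated SSI eyes and an unsourced 8 mmHg, and they describe one of two tests that must both succeed. Nor does the point extend to the optional mITT methods for eyes without an SSI, which are not the primary analysis.

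**What to change.** In Section 11.4.1:

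- State which IOP value is carried forward for SSI eyes, and that a reading taken on IOP-lowering medication is not an unmedicated value.
- Pre-specify a re-test of the first co-primary in which each SSI eye with a medicated last reading before the SSI takes the higher of that reading and its baseline unmedicated diurnal IOP. Show it beside the current rule, and qualify any claim of success on this endpoint if the two disagree.
- Report the number of SSI eyes by medication status at the last reading, using the medication log (Table 1) and the drug list recorded with each IOP (Section 20.5).

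The cost is SAP wording, one derived flag and one extra analysis from data the protocol already collects. The re-test is deliberately conservative and loses power if there are several such eyes: about 71% with three and 60% with six under the 3 mmHg assumption in step 5. It therefore need not replace the primary analysis.

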9.9 MANAGEMENT OF IOP AFTER SURGERY

This protocol recommends that no IOP-lowering medications should be administered to subjects after the surgery (0 meds on postop day 1) unless medically warranted. Investigators should use their clinical judgement in determining when and why IOP-lowering medications should be reintroduced and if a subject requires surgical re-intervention to manage IOP.

Re-introduction of hypotensive medications should follow the guidelines below:

- The same medication class(es) as used preoperatively should be re-introduced. Dependent on preoperative IOP medication use, the reintroduction/addition of IOP medications postoperatively should follow the order below:
 1. Prostaglandin Analogues
 2. Alpha Agonists
 3. Beta Blockers
 4. Rho Kinase Inhibitor
 5. Carbonic Anhydrase Inhibitors (CAIs)
- No more than one ocular hypotensive agent should be added at a single visit or within a 2-week period.

³² 180° trabeculotomy should be attempted in every eye enrolled in the study. There is a possibility that 180° trabeculotomy may not be possible in each case.

In the event of a steroid response (IOP increase), the usual guidelines requiring a reproducible increase in IOP should be followed; however, topical hypotensive medications should be discontinued once the topical steroid has been discontinued.

If a pressure rise is observed, a paracentesis may be performed as necessary. If a paracentesis is performed and there is no protocol-defined adverse event, the paracentesis will be documented in the subject's medical record, the applicable visit CRF and the Ocular Procedures log. If, however, the paracentesis is performed in conjunction with an AE, then the AE is recorded as such, and the paracentesis is also recorded on the AE CRF as a treatment for the protocol-defined AE (as well as the other CRFs mentioned above).

Medications which have been re-started by the investigator may be discontinued if the investigator's judgment is that the target intraocular pressure has been reached and the continued use of some or all of the therapy may not be required. Discontinuation of medications after re-introduction is recommended to be in the reverse order of re-introduction. The rationale for discontinuation will also be documented on the follow-up form by the investigator.

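### An eye re-operated to control IOP can be scored as a medication reduction in the second co-primary, because its last drop count before that surgery becomes its 12-month value

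*Combined protocol and SAP*

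**What the plan says.** All places are in the combined protocol and SAP.

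- **Endpoint and test.** The second co-primary is the reduction in number of IOP-lowering medications from screening to 12 months (7.1). It is tested against a null mean reduction of 0.75, and both co-primaries must be met (11.1.1).
- **SSI eyes in the primary analysis.** Section 11.4.1 introduces both co-primaries together. For eyes with an SSI to control IOP, or one that can affect IOP, it then says "the last available observed data before the SSI will be used to impute the 12-month data", without separating IOP from drop count. Under 11.2, "mITT subjects with an uneventful study procedure but with SSIs before the 12-month visit will be included in the PP population", and PP is the primary analysis set.
- **SSI eyes in the secondary analyses.** Section 9.9: "Subjects who have a secondary IOP-lowering intervention will be considered treatment failures for the purpose of the secondary endpoint analyses". Section 11.4.2: "the non-responder (i.e. do not achieve the secondary effectiveness endpoint) will be assumed for the missing 12-month response".
- **Other imputations.** The worst-value, mean and last-observation options in 11.4.1 are for mITT only and are introduced by "the following imputation for subjects with missing 12-month data but without SSI may be performed".
- **Drops after surgery.** Section 9.9: "This protocol recommends that no IOP-lowering medications should be administered to subjects after the surgery (0 meds on postop day 1) unless medically warranted" and "No more than one ocular hypotensive agent should be added at a single visit or within a 2-week period". Inclusion criterion 4 requires 1 to 4 medications at screening.

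**The concern.** After the study surgery the drop count starts at a recommended zero and is rebuilt in steps. If an eye is re-operated for uncontrolled IOP before that rebuilding is complete, its last pre-SSI count reflects how little time has passed, not how well the procedure worked. Take an eye on 3 drugs at screening, restarted on 1, and re-operated at week 3. Under 9.9 it is later withdrawn, so it has no 12-month visit. Under 11.4.1 it enters the medication co-primary as a reduction of 2, well above the 0.75 threshold, while it is a failure on both secondary endpoints.

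The contrast with ordinary missing data is also awkward. Under the worst-value options, an mITT eye with no SSI and no data after month 3 falls back to its baseline value. A known surgical failure can therefore score better than an eye that is merely missing. At stake is a non-inferiority test that gates the study's claim, where scoring choices should not lean towards the device.

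**Working it through.** **Inputs from 11.1.1.** Null 0.75, planned alternative 1.0 (distance 0.25), SD 1.0, one-sided 0.025, one-sample t-test, 116 evaluable eyes.

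**Assumed.** The documents give neither an SSI rate nor a drop count at SSI. I take k SSI eyes, each r drugs below its screening count.

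**Step 1: the plan's own figures.** Exact power from the noncentral t distribution.
- IOP co-primary: difference 1.0, SD 3.8, n = 116 gives 80.3%. The stated 116 reproduces.
- Medication co-primary: difference 0.25, SD 1.0 needs 128 eyes at one-sided 0.025. The stated 101 does not reproduce at that level; it is the answer at one-sided 0.05. Power at 116 eyes is 76%. This is a separate matter and does not affect the point here.

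**Step 2: shift in the mean.** If an SSI eye should count as no reduction but is credited r, the mean rises by k × r / 116.
- One eye: 1/116 = 0.009, 2/116 = 0.017, 3/116 = 0.026, or 3%, 7% and 10% of the 0.25.
- 2 eyes × 1 drug: 2/116 = 0.017 (7%).
- 3 eyes × 2 drugs: 6/116 = 0.052 (21%).
- 6 eyes × 2 drugs: 12/116 = 0.103 (41%).

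**Step 3: chance of passing the medication test.** Suppose the mean with SSI eyes at zero is exactly 0.75. Under carry-forward the noncentrality is (k × r / 116) × √116 / 1.0, and the critical t on 115 df is 1.981.

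| SSI eyes × credit | Noncentrality | Chance of passing |
|---|---|---|
| none | 0 | 2.5% |
| 1 × 1 | 0.09 | 3.1% |
| 2 × 1 | 0.19 | 3.8% |
| 3 × 2 | 0.56 | 8.0% |
| 6 × 2 | 1.11 | 19.6% |

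**Step 4: check by simulation.** The table keeps the SD at 1.0. Placing the SSI eyes explicitly in the sample (SD 1.0 in the others, 400,000 trials) gave 3.8%, 7.6% and 18.7% for the last three rows. Scoring those eyes zero gave 2.2% to 2.4%.

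**Step 5: when the rule can change the result.** The test passes when the observed mean exceeds about 0.75 + 1.981/√116 = 0.934. The scoring rule decides the outcome only if the mean lies within the shift of that value.

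**The case against.** - **It is a choice of estimand.** A reader might take 8.0% or 19.6% as the type I error of the plan. The documents do not support that. For the quantity the plan targets, the value before SSI, this argument shows no inflation. The figures apply only if an SSI eye is defined as zero reduction. This stands, and they are stated on that condition.
- **The threshold's sources.** The 0.75 derives from cataract-only reductions of 0.9 and 1.1 in two earlier studies. How those studies scored eyes with secondary surgery is not stated. If they used pre-SSI values, a failure score here would not be like for like. This stands as a caveat.
- **Few drops is not shown to be usual.** A reader might infer that re-operated eyes generally carry fewer drops than at screening. Section 9.9 permits drops when medically warranted and leaves timing to the investigator. An eye entering on one drug can regain its count in one step. An eye back on its full regimen gets no credit, and one above it already scores negative. Nothing says SSIs cluster early. What remains is that the credit can arise.
- **The IOP co-primary.** A reader might infer that failures help the study as a whole. The same carry-forward applies to IOP and may hurt there. As an illustration, let six eyes carry zero IOP reduction and the other 110 average 7.5 mmHg. The mean is 7.5 × 110/116 = 7.11, and IOP power falls from about 80% to about 40% (SD held at 3.8). Which IOP would be carried is unclear, because unmedicated diurnal IOP is scheduled only at baseline and 12 months. So no study-level inflation is shown.
- **Visibility elsewhere.** Section 11.4.4 stratifies the 12-month IOP distributions by medication change and SSI and plans a Kaplan-Meier curve for SSI; need for SSI is a listed adverse event. These show that failures occurred but do not change the co-primary's value.

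**Conclusion.** The point holds in conditional form. Under 11.4.1, an eye re-operated to control IOP while below its screening drop count is scored as a medication reduction in a gating non-inferiority test. The plan treats the same eye as a failure elsewhere, and none of its listed sensitivity analyses tests this scoring.

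The size depends on unknowns. One or two SSI eyes, each credited one to three drugs, move the mean by 0.009 to 0.052. Six eyes credited two drugs each move it by 0.103, or 41% of the distance from null to alternative. The passing probabilities above concern the medication test alone and assume that zero reduction is the right score.

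This is a should-fix. A mandatory change is not supported, because the effect may be small, the current rule is prespecified and definable, and the IOP co-primary must also be met.

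**What to change.** In 11.4.1, for the medication co-primary only and in both PP and mITT:

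- For an eye with an SSI performed to control IOP, set the 12-month count to the larger of its screening count and its last pre-SSI count, so that the reduction is no greater than zero.
- For an SSI done for another reason that can affect IOP, keep the last pre-SSI count. Such an eye is not a failure of IOP control; one off all its drugs at month 9 should not be scored zero because of unrelated surgery.
- Report the current rule for all SSI eyes as a sensitivity analysis.

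The reference count should be the screening count, as 7.1 defines the endpoint. Section 11.4.1 measures the medication reduction from baseline, which follows washout, so that wording should be aligned in the same edit.

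The cost is a sentence or two of SAP text, settled before 12-month data are analysed. It needs no new visits or measurements and no change to patient management. The downside is a slightly less favourable mean reduction. The SAP should also acknowledge that SSI handling in the studies behind the 0.75 threshold is not stated.
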